7.1 DISCONTINUATION OF STUDY TREATMENT

For data to be collected at the time of treatment discontinuation and follow-up and for any further evaluations that need to be completed see the SoA (Section [1.3](#)).

Reasons for discontinuation of study treatment (or withdrawal from the study) may include, but are not limited to, the following:

- Participant withdrawal of consent at any time.
- Any toxicity, which is not manageable with dose delays, dose decrease, and appropriate treatment
- Any medical condition that the Investigator or Sponsor determines may jeopardize the participant's safety if he or she continues in the study.
- Investigator or Sponsor determination that treatment discontinuation is in the best interest of the participant.
- Pregnancy
- Disease progression when there is a consensus that the participant will not benefit from further study treatment
- Immunoglobulin E (IgE)-mediated hypersensitivity reactions, including anaphylaxis.
- Any event that meets stopping criteria defined in Section [4.1.3](#).

Participants who discontinue study treatment prematurely will be asked to return to the clinic for a study completion/early termination visit (see Section [8.11.3](#)) and may undergo follow-up assessments (see Section [8.11.4](#)), unless the participant withdrew consent.

The primary reason for premature study treatment discontinuation should be documented on the appropriate eCRF.

Treatment beyond Disease Progression

- As with other immunotherapies, treatment beyond RECIST v1.1 progression may be considered following discussion between the Investigator and the Sponsor.
- The criteria below are needed for continuing treatment beyond initial apparent progressive disease per RECIST v1.1 (e.g., radiological progression secondary to tumor inflammation):
 - Absence of clinical deterioration or improvement in clinical symptoms.
 - Investigator-assessed potential clinical benefit for the participant.
 - The participant is tolerating study drug.

Participant Replacement Rules

Participants who discontinue study treatments prematurely may be replaced for the following reasons to ensure adequate numbers of evaluable participants:

- For all parts: Participants who withdraw from the study prior to the treatment start may be replaced.
- For Part I:
 - Participants who discontinue from the study before the end of the DLT period for reasons other than DLTs.

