7.2 PARTICIPANT DISCONTINUATION/WITHDRAWAL FROM THE STUDY

Participants have the right to withdraw voluntarily from the study at any time for any reason. In addition, the Investigator has the right to withdraw a participant from the study for medical conditions that the Investigator or Sponsor determines, may jeopardize the participant's safety if he/she continues in the study.

If possible, information on reason for withdrawal from the study should be obtained. The primary reason for withdrawal from the study should be documented on the appropriate eCRF. Participants will not be followed for any reason after consent has been withdrawn.

When a participant voluntarily withdraws from the study, or is withdrawn by the Investigator, samples collected until the date of withdrawal will be analyzed, unless the participant specifically requests for these to be discarded or local laws require their immediate destruction. However, if samples have been tested prior to withdrawal, results from those tests will be used as part of the overall research data. A participant's withdrawal from this study does not, by itself, constitute withdrawal of samples donated to the Research Biosample Repository (RBR).

Participants who withdraw from the study for safety reasons will not be replaced. Participants who withdraw from the study for other reasons may be replaced as described in Section 7.

For data to be collected at the time of study discontinuation and at safety and follow-up visits, and for any further evaluations that need to be completed, see the SoAs (Section 1.3).

Participants will be treated until progressive disease, unacceptable toxicities, or withdrawal of consent.

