8.3 ADVERSE EVENTS AND SERIOUS ADVERSE EVENTS

The definitions of an AE or SAE can be found in [Appendix 2](#). The NSAESI and disease-related events and/or disease-related outcomes not qualifying as AEs or SAEs are discussed in Sections [8.3.6](#) and [8.3.8](#).

The Investigator and any qualified designees are responsible for ensuring that all AEs (including assessment of seriousness, severity and causality; see [Appendix 2](#)) are recorded on the Adverse Event eCRF and reported to the Sponsor in accordance with instructions provided in this section and in [Appendix 2](#).

Procedures used for recording AEs are provided in [Appendix 3](#).

8.3.1 Time Period and Frequency for Collecting Adverse Event and Serious Adverse Event Information

The method of recording, evaluating, and assessing causality of AEs and SAEs and the procedures for completing and transmitting SAE reports are provided in [Appendix 2](#).

Investigators will seek information on AEs at each participant's contact. All AEs, whether reported by the participant or noted by study personnel, will be recorded in the participant's medical record and on the Adverse Event eCRF as follows:

After informed consent has been obtained **but prior to initiation of study treatment**, only SAEs caused by a protocol-mandated intervention should be reported (e.g., SAEs related to invasive procedures such as biopsies). Any other AE should not be reported.

After initiation of study treatment, all AEs, regardless of relationship to study treatment, will be reported until the safety follow-up visit, or participant discontinuation, whichever occurs first. DLTs will be reported during the DLT assessment window.

Post-study AEs and SAEs: The Investigator is not required to actively monitor participants for AEs after the end of the AE reporting period – that is, after the safety follow-up visit.

However, if the Investigator learns of any SAE (including a death) or other AEs of concern that are believed to be related to prior treatment with study treatment, at any

time after a participant has been discharged from the study, and the Investigator considers the event to be reasonably related to the study treatment or study participation, the Investigator must promptly notify the Sponsor. For the procedure of reporting, see [Appendix 2](#).

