8.11.3 Assessments at Study Completion/Early Termination Visit

End of Treatment/Early Discontinuation: Participants who complete the treatment or discontinue from the study early, will be asked to return to the clinic 28 (\pm 7) days after the last dose of study drug or last data point. The visit at which a response assessment shows progressive disease may be used as the Early Discontinuation visit. Assessments should be completed as detailed in the SoA (Section 1.3).

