8.11.4 Follow-Up Assessments

Safety Follow-Up/End of Study: Participants who complete the treatment or discontinue from the study early, will be asked to return to the clinic 135 (\pm 30) days after the last dose of study drug or last data point determined for an End of Treatment Visit. Assessments should be completed as detailed in the SoA (Section 1.3).

Survival Follow-Up: The sites will provide to the Sponsor (using a designated section of the eCRF) with an update on survival status 90 (\pm 7) days after the Safety Follow-Up visit and then every 3 months (\pm 2 weeks) thereafter up until 24 months post initial treatment (or until study closure) for each participant enrolled in the study. Patients who screen-failed due to the ROPRO score will also be followed up for survival.

After the study completion/early termination visit, AEs should be followed as outlined in Sections 8.3.1 and 8.3.3.

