For reports of serious adverse events and non-serious adverse events of special interest (Section 8.3.6) that occur after initiation of study treatment (Section 8.3.1), investigators should record all case details that can be gathered immediately (i.e., within 24 hours after learning of the event) on the appropriate Adverse Event of Special Interest/ Serious Adverse Event eCRF form and submit the report via the electronic data capture (EDC) system. A report will be generated and sent to the Sponsor's Safety Risk Management department.

In the event that the EDC system is unavailable, the Serious Adverse Event/Adverse Event of Special Interest Reporting Form provided to investigators should be completed and submitted to the Serious Adverse Event Responsible immediately (i.e., no more than 24 hours after learning of the event).

Once the EDC system is available, all information will need to be entered and submitted via the EDC system.

Reporting of Post-Study Adverse Events and Serious Adverse Events

After the end of the adverse event reporting period (see Section 8.3.1), all deaths, regardless of cause, should be reported through use of the Long-Term Survival Follow-Up eCRF.

In addition, if the Investigator becomes aware of a SAE that is believed to be related to prior study treatment, the event should be reported directly to the Sponsor or its designee, either by faxing or by scanning and emailing the SAE Reporting Form using the fax number or email address provided to investigators.

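### Section 8.3.1 can close reporting of all adverse events before the 135-day safety visit for participants who leave the study early but have not withdrawn consent

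*Combined protocol and SAP*

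**What the plan says.** Section 8.3.1 sets the operative rule. From the start of study treatment, all AEs, whether or not related, "will be reported until the safety follow-up visit, or participant discontinuation, whichever occurs first". The following paragraph, on post-study events, releases the Investigator from active monitoring once the reporting period is over and glosses that moment as "that is, after the safety follow-up visit", with no mention of discontinuation.

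The visit sections include people who leave early. Section 8.11.3 sets the End of Treatment/Early Discontinuation visit, counted in days from final dosing with a window of ±7: "Participants who complete the treatment or discontinue from the study early, will be asked to return to the clinic 28". Section 8.11.4 does the same for the safety follow-up visit, with a window of ±30: "Participants who complete the treatment or discontinue from the study early, will be asked to return to the clinic 135". Section 7.1 is softer. Those who stop treatment prematurely come back for an early termination visit "and may undergo follow-up assessments", unless consent was withdrawn.

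Section 7.2 covers leaving the study. Besides voluntary withdrawal, "the Investigator has the right to withdraw a participant from the study for medical conditions" that may jeopardise safety. It rules out follow-up only once consent has been withdrawn.

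For the time after the reporting period, Appendix 2, Section 5.1 records all deaths and provides for reporting "if the Investigator becomes aware of a SAE that is believed to be related to prior study treatment". Section 8.3.1 adds prompt notification of other related AEs of concern that the Investigator learns of.

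**The concern.** The nature and frequency of AEs is a primary endpoint in all three Parts (Table 4). Table 13 keeps every treated participant in the safety population, including those withdrawn prematurely. If a participant's all-AE reporting ends at study discontinuation, that person stays in the denominator while new events before the 135-day visit need not be recorded. Any error runs in one direction, towards under-counting.

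The affected group includes people whom the Investigator withdraws for medical reasons. Sections 2.3 and 8.3.9 name overlapping immune-mediated toxicity as a concern for a combination given to humans for the first time, so an ambiguous end to AE collection matters here. Two sites could also apply the two sentences of Section 8.3.1 differently and produce AE rates that are not comparable.

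**Working it through.** The plan gives no statistical figure to reproduce. The check sets the provisions side by side and does day arithmetic on the visit windows.

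**Step 1. Where does all-AE reporting end?**

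| Place | End of reporting, or expected contact |
|---|---|
| 8.3.1, operative sentence | Safety follow-up visit or participant discontinuation, whichever is earlier |
| 8.3.1, next paragraph | Safety follow-up visit only |
| 8.11.3 | Early leavers asked back at 28 ± 7 days |
| 8.11.4 | Early leavers asked back at 135 ± 30 days; AE handling referred back to 8.3.1 and 8.3.3 |
| 7.2 | No follow-up after consent withdrawal; otherwise points to the schedule for data at discontinuation and at safety visits |

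For someone who discontinues before the safety visit, the first two rows cannot both be followed. Section 8.11.4 refers back to 8.3.1, so it does not settle the matter.

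**Step 2. Who is affected?** Section 7 treats stopping study treatment (7.1) separately from participant discontinuation or withdrawal from the study (7.2). On that usage:

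- Stops treatment only: reporting continues to the safety visit, so the gap is 0 days.
- Withdraws consent: no follow-up is allowed, so nothing further could be collected.
- Leaves the study without withdrawing consent and still returns: this is the affected group.

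**Step 3. How long is the interval for an affected participant?**

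- Safety visit: 135 − 30 = 105 to 135 + 30 = 165 days after the last dose.
- End of Treatment visit: 28 − 7 = 21 to 28 + 7 = 35 days after the last dose.
- If reporting stopped at the last dose: 105 to 165 days uncovered, nominally 135.
- If it stopped at the End of Treatment/Early Discontinuation visit: 105 − 35 = 70 to 165 − 21 = 144 days, nominally 135 − 28 = 107.

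The date of discontinuation decides where a given participant falls.

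**Step 4. What is still captured in that interval?**

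- All deaths (Appendix 2, Section 5.1).
- Related serious AEs that the Investigator becomes aware of (Appendix 2, Section 5.1; 8.3.1).
- Other related AEs of concern that the Investigator learns of (8.3.1).
- The course of AEs already reported, which Section 8.3.3.1 follows without making discontinuation an end-point.

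This leaves new unrelated AEs and serious AEs, related non-serious AEs not judged of concern, and related events that never come to the Investigator's notice.

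**The case against.** The best defence is that this is loose drafting with little consequence. The headings of Sections 7.1 and 7.2 give the term a natural meaning, leaving the study. Most participants will stop treatment for progression or toxicity and stay under full reporting. The second paragraph of 8.3.1 suggests that the safety visit was always the intended end. AEs are asked about at every contact, known AEs are followed up, and related events of concern must be notified at any time. The 135-day visit is a request and not an obligation, so some early leavers would not attend in any case.

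Much of this stands, and it limits the size of the point. It does not remove the conflict. The post-study route is passive and depends on a judgement of relatedness. Asking at each contact does not help, because recording is governed by the same cut-off. The second paragraph shows that 8.3.1 is inconsistent, but a site cannot tell which sentence prevails.

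A reader might go further and infer that all-AE reporting ends when treatment stops, so that nearly everyone who progresses loses the whole follow-up period. Usage elsewhere invites this: Section 8.1.1 lets the visit showing progression serve as the discontinuation visit, and Section 7.1.1 counts the treatment period up to a discontinuation visit. The structure of Section 7 points the other way, so that reading is not supported.

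**Conclusion.** The inconsistency is real and bears on a primary endpoint, but its reach is narrow. Under the literal rule, all-AE reporting can close before the 135-day visit for participants who leave the study without withdrawing consent, although that visit is still planned for them and they remain in the safety population. For such a participant, the uncovered time is nominally 107 days if reporting ends at the early discontinuation visit, and at most 165 days if it ends at the last dose.

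This rests on two assumptions: that participant discontinuation means leaving the study, as in Section 7.2, and that the participant does return when asked. The adverse event row of Table 1 could not be read reliably in the available text, so nothing here depends on it.

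Two stronger conclusions do not follow. One is that all late events go unreported: deaths, and related serious events or related events of concern that come to the Investigator's notice, are still captured. The other is that the safety endpoint is biased by a material amount: the documents give neither the number of such participants nor their event rate, so only the direction of any error can be stated.

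**What to change.** In Section 8.3.1, state that all AEs are reported until the safety follow-up visit, including for participants who discontinue treatment or are withdrawn by the Investigator, and that reporting ends earlier only at withdrawal of consent, death or loss to follow-up. This replaces the undefined term and agrees with the next paragraph of the section. In Section 7.1, bring "may undergo follow-up assessments" into line with Section 8.11.4, where early leavers are asked to return.

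The cost is protocol wording and somewhat more AE entries during follow-up, some of them unrelated to study drug. The visits are already scheduled, so no new contact is needed.

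Separately, reconcile the window of the safety follow-up visit. It is ±30 days in Sections 4.1.1 and 8.11.4 and in Table 1, but ±35 days in the end-of-study definition of the synopsis and Section 4.4 (135 − 35 = 100 to 135 + 35 = 170 days). This mismatch does not cause the reporting gap, but it concerns the visit that closes reporting and can be settled in the same amendment.

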8.3.2 Method of Detecting Adverse Events and Serious Adverse Events

Care will be taken not to introduce bias when detecting AEs and/or SAEs. Open-ended and non-leading verbal questioning of the participant is the preferred method to inquire about AE occurrence.

A consistent methodology of non-directive questioning should be adopted for eliciting AE information at all participant evaluation timepoints.

8.3.3 Follow-Up of Adverse Events and Serious Adverse Events

8.3.3.1 Investigator Follow-Up

The Investigator should follow each AE until the event has resolved to baseline grade or better, the event is assessed as stable by the Investigator, the event is otherwise explained, the participant is lost to follow-up (Section [7.3](#)), or the participant withdraws consent. Every effort should be made to follow all SAEs considered related to study treatment or study-related procedures until a final outcome can be reported.

During the study period, resolution of AEs (with dates) should be documented on the Adverse Event eCRF and in the participant's medical record to facilitate source data verification. If, after follow-up, return to baseline status or stabilization cannot be established, an explanation should be recorded on the Adverse Event eCRF.

All pregnancies reported during the study should be followed until pregnancy outcome and reported according to the instructions provided in Section [8.3.5](#).

8.3.3.2 Sponsor Follow-Up

For SAEs, NSAESIs, and pregnancies, the Sponsor or a designee may follow up by telephone, fax, electronic mail, and/or a monitoring visit to obtain additional event details and outcome information (e.g., from hospital discharge summaries, consultant reports, autopsy reports) in order to perform an independent medical assessment of the reported event.

8.3.4 Regulatory Reporting Requirements for Serious Adverse Events

Prompt notification by the Investigator to the Sponsor of an SAE is essential so that legal obligations and ethical responsibilities towards the safety of participants and the safety of a study treatment under clinical investigation are met.

The Sponsor has a legal responsibility to notify both the local regulatory authority and other regulatory agencies about the safety of a study treatment under clinical investigation. The Sponsor will comply with country-specific regulatory requirements relating to safety reporting to the regulatory authority, IRB/IEC, and investigators.

Investigator safety reports must be prepared for suspected unexpected serious adverse reactions according to local regulatory requirements and Sponsor policy and forwarded to investigators as necessary.

An Investigator who receives an Investigator safety report describing an SAE or other specific safety information (e.g., summary or listing of SAEs) from the Sponsor will review and then, file it along with the IB and will notify the IRB/IEC, if appropriate according to local requirements.

For immediate and expedited reporting requirements from Investigator to Sponsor and from Sponsor to Health Authority, investigators, IRB, and IEC, see [Appendix 2](#).

8.3.4.1 Emergency Medical Contacts

To ensure the safety of study participants, access to the Medical Monitors is available 24 hours a day 7 days a week. Details will be available separately.

8.3.5 Pregnancy

Female participants of childbearing potential will be instructed to immediately inform the Investigator if they become pregnant during the study or within 4 months after the last dose of RO7296682/atezolizumab.

Male participants will be instructed through the ICF to immediately inform the Investigator if their partner becomes pregnant during the study or within 28 days after the final dose of RO7296682.

If a pregnancy is reported, the Investigator should inform the Sponsor within 24 hours of learning of the pregnancy and should follow the pregnancy reporting process as detailed in [Appendix 5](#).

Abnormal pregnancy outcomes (e.g., spontaneous abortion, fetal death, stillbirth, congenital anomalies, and ectopic pregnancy) are considered SAEs ([Appendix 5](#)).

